#### **4.3 OTHER SCREENING CONSIDERATIONS**

- Subjects not enrolled in the PK subset must be willing and agree to return to the clinical investigative site for follow-up visits on Day 7, Day 14, and Day 21 (+1 day), a dosing complete visit on Day 29 or ET visit, and answer follow-up telephone calls on Day 42 (+2 days) and on Day 58 (+2 days).
- Subjects in the PK subset must be willing and agree to return to the clinical investigative site for 3 separate dosing and PK periods, for follow-up visits on Day 7 and Day 21, and answer follow-up telephone calls on Day 42 (+2 days) and on Day 58 (+2 days).
- Subjects must be willing to fast for 8 hours prior to specimen collection of the fasting lipid panel that will be performed at screening.

- Subjects must be willing to take study drug within 30 minutes after eating a meal containing approximately 600 calories and 25 g of fat.
- Subjects must be willing to take study drug at home for 28 days and record the date and time in a subject diary.
- Subjects must be willing to record information related to TPOXX or matching TPOXX placebo, concomitant medications, AEs, and meal compliance in their subject diary.

## **4.4 WITHDRAWAL OF SUBJECTS FROM THE STUDY**

### **4.4.1 Reasons for Withdrawal**

Under certain circumstances, a subject may be terminated from participating in the study based on the opinion of the investigator, SIGA, FDA, and/or the Data Safety Monitoring Board (DSMB). Subjects will be withdrawn from the study if they do not meet the study inclusion and exclusion criteria before dosing of the study drug.

Subjects can withdraw consent and discontinue from the study at any time, for any reason, without prejudice to further treatment.

The investigator may withdraw a subject from the study for any of the following:

- Subject is in violation of the protocol.
- Subject experiences a serious or intolerable AE that in the investigator's opinion requires withdrawal from the study.
- Subject becomes pregnant.
- Subject is noncompliant.
- Subject has laboratory abnormalities for assessments listed in [Sections 4.1](#) or [Section 4.2](#) that meet grade 3 or grade 4 on the Division of Acquired Immune Deficiency Syndrome AE Grading Table; any other grade 3 or grade 4 AE; or a grade 2 or higher rash considered by the investigator to be possibly, probably, or definitely related to study drug.
- Subject develops, during the course of the study, symptoms or conditions listed in the exclusion criteria.

- Subject develops during the course of the study, laboratory abnormalities listed in the exclusion criteria.
- Subject requires a medication prohibited by the protocol.
- Subject requests an early discontinuation for any reason.
- Subject's primary care provider requests that the subject be withdrawn.
- The FDA, SIGA, or the DSMB requests subject withdrawal based on study safety findings.

The investigator can also withdraw a subject upon the request of SIGA or if SIGA terminates the study. Upon occurrence of an SAE or intolerable AE, the investigator will confer with the medical monitor and with SIGA. If a subject is discontinued because of an AE, the event will be followed until it is resolved or stabilized as determined by the investigator and/or the medical monitor.

#### **4.4.2 Handling of Withdrawals**

Subjects are free to withdraw from the study at any time upon request. Subject participation in the study may be stopped at any time at the discretion of the investigator or at the request of SIGA.

When a subject withdraws from the study, the reason(s) for withdrawal will be recorded by the investigator in the electronic case report form (eCRF). Whenever possible, any subject who withdraws from the study prematurely will undergo all ET visit assessments ([Table 9-1](#) and [Table 9-2](#)). A blood sample will be collected for all subjects who discontinue from the study for TPOXX plasma concentration analysis *if the ET visit occurs within 30 hours after the subject's last dose of TPOXX/matching placebo* in order to collect information about the relationship between TPOXX blood level and ET from the study. Any subject who fails to return for final assessments will be contacted by the site in an attempt to have them comply with the protocol. The status of subjects who fail to complete final assessments will be documented in the eCRF.

#### **4.4.3 Halting Rules**

Safety evaluations will include: medical history, body weight, physical assessments, vital sign measurements, routine laboratory test results, ECG results, and AEs reported by

subjects. Symptom-directed or targeted physical examinations may be performed if indicated by interim complaints or laboratory findings.

The medical monitor and investigator will closely monitor and analyze study data as they become available and will make determinations regarding the presence and level of AEs. The medical monitor will provide an independent review of the AEs that have a bearing on study stopping. All AEs determined by the investigator to be severe and possibly, probably, or definitely related to study drug, as well as all clinical assessments, laboratory test results, ECG results, or vital sign measurements that meet grade 3 criteria on the DAIDS AE Grading Table will be assessed by the medical monitor, who will make a recommendation as to whether or not temporary halting of the study should occur.

The study will be temporarily halted (no new enrollments and no further study drug dosing) by the medical monitor or designee by promptly notifying the investigators and the DSMB (as outlined in the DSMB charter) according to the following criteria:

- One subject experiences a grade 4 AE assessed as possibly, probably, or definitely related to study drug.
- There is a subject death that is assessed as possibly, probably, or definitely related to study drug.
- One subject experiences a seizure that is assessed as possibly, probably, or definitely related to study drug.
- Two or more subjects experience the same or similar SAEs that are possibly, probably, or definitely related to the study drug.
- Three or more subjects experience the same or similar AEs that are DAIDS grade 3 or above and are possibly, probably, or definitely related to the study drug.
- Three or more subjects have clinically significant laboratory abnormalities that meet DAIDS grade 3 or above criteria.

Investigators will advise SIGA immediately if any of the halting rules are met and SIGA will notify the FDA immediately.

Study enrollment and study drug dosing would resume if review of the AEs that caused the halt resulted in a recommendation to permit further continuation. In such an instance, SIGA, with participation by the investigator and the medical monitor would consult with the DSMB and review all AEs that meet the criteria for halting the study. The study would remain suspended until the events were reviewed by the DSMB and recommendation was made as to

whether the study would be continued or stopped. This constitutes a minimum criterion, and the decision to halt the study may be made based on any other criteria that, in the judgment of the investigator, with agreement of the medical monitor, indicate a potentially serious safety concern. Investigators will advise SIGA immediately if any of the halting rules are met. Safety oversight for this study is discussed in [Section 9.3.3.1.4](#).

#### **4.4.4 Replacements**

At the discretion of the investigator, and after consultation with the medical monitor and SIGA, any subject who withdraws before completing the study may be replaced. Any replacement subject will be assigned to the same treatment as the subject they are replacing.

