## **5.3 METHOD OF ASSIGNING SUBJECTS TO TREATMENT GROUPS**

Randomization will be performed using an interactive web response system (IWRS). The randomization will be balanced by using permuted blocks of an appropriate size and be stratified by age group (18 to 30 years, 31 to 45 years, 46 to 64 years, and 65 to 80 years). In the event of the withdrawal of a clinical investigative site, no adjustments to the randomization scheme will be implemented because site will not be used as a stratification factor. After a randomization number has been assigned, it will not be reused.

The PK subset of 40 subjects will be enrolled at up to 2 sites with at least 32 subjects who will receive TPOXX and at least 8 subjects who will receive placebo. Of the remaining subjects who are not enrolled in the PK subset, at least 324 subjects will be randomly assigned to receive TPOXX and 81 subjects to receive placebo. The IWRS will facilitate the random assignment of treatment for subjects in the study. Randomization will occur before study drug administration on Day 1, after it has been confirmed that the subject fulfills all eligibility criteria. The IWRS will assign a randomization number that is used to link the subject to 1 of the 2 treatment groups using a 4:1 ratio based on a computer-generated central randomization schedule prepared before enrollment. The IWRS will also specify the study

drug bottle numbers to be assigned to the subject where the study drug bottle numbers match the treatment group assigned by the randomization list. The assigned study drug bottles will be dispensed to the subject by the clinical investigative site. The randomization code will not be broken or made available to study subjects or their families, investigators, clinical personnel, or site managers until all subjects have completed the double-blind phase of the study and the database has been closed in accordance with the clinical investigative sites standard operating procedures (SOPs).

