## **5.4 BLINDING**

### **5.4.1 Blinding Procedures**

This study will be performed as a double-blind study. All parties involved in the study except for the medical monitor (in the event of a suspected unexpected serious adverse reaction) and the unblinded statistician for DSMB Closed Session meetings, will remain blinded to the treatment until study completion. Under routine circumstances, the blind will not be broken.

TPOXX and matching placebo capsules are indistinguishable and all study drug bottles will be packaged the same way. Study drug bottle labeling will include all required identifying information except for the identity of the study treatment.

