### **5.4.2 Breaking the Blind**

The medical monitor will be responsible for maintaining the blind throughout the study. If a subject becomes seriously ill or pregnant during the study, the blind will be broken only if knowledge of the administered study drug will affect that subject's available treatment options. In the event of a medical emergency requiring identification of the study drug administered to an individual subject, the investigator will make every attempt to contact the medical monitor to explain the need for opening the code within 24 hours of unblinding the subject's randomization assignment. The investigator will be responsible for documenting the time, date, reason for the code break, and the names of the personnel involved. All unblinding activities will be tracked via an audit trail in IWRS. Requests for unblinding of a subject's randomization assignment will be made through the IWRS after consultation with the medical monitor. Subject code breaks by the investigator will result in withdrawal of the subject from the study. The date, time, and reason for the unblinding must be documented on the appropriate page in the eCRF, and SIGA must be informed as soon as possible. The treatment assignment of subjects will remain blinded until all clinical evaluations have been completed. Unblinding at the end of the study will occur only by written request from the

lead statistician to the unblinded randomization statistician and the unblinded IWRS team after database lock and confirmation of protocol deviations. The DSMB may request to unblind the treatment assignment of a subject or the study at any time.

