### **Pooling of Sites**

Up to 10 sites in the USA will be used in this study. The PK subset will be enrolled at 1 Phase 1 unit. For the remaining sites, a maximum number of subjects will be agreed upon and enrollment

will be competitive. Thus major differences in subject enrollment numbers per site are not expected, and therefore there will be no inter-subject pooling of data.

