### **4.3. Randomization, Stratification, and Blinding**

Healthy subjects will be randomized to receive:

- Treatment Group 1: An oral dose of 600 mg ( $3 \times 200$ -mg capsules) TPOXX BID (every 12 hours [ $\pm 30$  minutes]) for subjects with a body weight of 120 kg or less or TID (every 8 hours [ $\pm 30$  minutes]) for subjects with a body weight more than 120 kg for 28 days (Day 1 to Day 28).
- Treatment Group 2: An oral dose of placebo (3 capsules identical to TPOXX) BID (every 12 hours [ $\pm 30$  minutes]) for subjects with a body weight of 120 kg or less or TID (every 8 hours [ $\pm 30$  minutes]) for subjects with a body weight more than 120 kg for 28 days (Day 1 to Day 28).

Randomization will occur according to the randomization schedule and will happen before the study drug administration on Day 1 after informed consent has been obtained and after it has been confirmed that the subject fulfills all eligibility criteria. Subjects will be randomly assigned to 1 of 2 treatment groups using a 4:1 ratio so that 4 subjects will receive TPOXX and 1 subject will receive placebo. This will be based on a randomization schedule prepared by a PPD biostatistician before the study. The groups will be stratified by age groups (18 to 30 years, 31 to 45 years, 46 to 64 years, and 65 to 80 years).

This study will employ a double-blind study design. Treatment assignment will not be known to the subjects, the Sponsor, the investigator, or the staff who are involved in the clinical evaluation of the subjects and the analysis of data. The randomization schedule will be generated by an unblinded randomization statistician at PPD according to PPD's standard operating procedures.

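### Protocol 4.4.4 passes a withdrawn subject's arm to the replacement even after an investigator code break, so a linked replacement at the same site can be enrolled with the arm already known

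*Combined protocol and SAP*

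**What the plan says.** **Replacement.** Under protocol 4.4.4, "any subject who withdraws before completing the study may be replaced". The investigator decides, after consulting the medical monitor and the sponsor. The arm is then fixed: "Any replacement subject will be assigned to the same treatment as the subject they are replacing". No reason for withdrawal is excluded.

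**Code breaks.** Protocol 5.4.2 says "Subject code breaks by the investigator will result in withdrawal of the subject from the study", and SAP 4.3 repeats the rule. Protocol 5.4.2 also makes the medical monitor responsible for the blind, routes unblinding requests through the IWRS after consultation with that monitor, keeps an audit trail and requires the sponsor to be told.

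**Blinding aims.** Protocol 5.3: "The randomization code will not be broken or made available to study subjects or their families, investigators, clinical personnel, or site managers" until the double-blind phase is complete and the database is closed. Protocol 5.4.1: with two named exceptions, neither of them the investigator, all parties "will remain blinded to the treatment until study completion". SAP 4.3: "Treatment assignment will not be known to the subjects, the Sponsor, the investigator, or the staff" involved in clinical evaluation or data analysis.

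**PK subset.** Protocol 5.3 places its 40 subjects at no more than two sites, "with at least 32 subjects who will receive TPOXX and at least 8 subjects who will receive placebo". The SAP, under Pooling of Sites, is narrower: "The PK subset will be enrolled at 1 Phase 1 unit".

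The randomisation sections (protocol 5.3 and SAP 4.3) describe no procedure for replacements. Neither document says whether a replacement must come from the same site, or whether the site is told which withdrawn subject a newcomer replaces.

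**The concern.** Each rule is reasonable alone. Together they allow a sequence that the plan does not address. An investigator breaks a code and learns the arm, the subject is withdrawn, the same investigator decides to replace that subject, and 4.4.4 gives the newcomer the arm just learned. Emergency unblinding is justified for the subject whose care depends on it. Nothing in the plan extends that justification to a new healthy volunteer.

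For such a newcomer both allocation concealment and investigator blinding could be lost. The investigator could decide whom to enrol knowing the arm, and would then record that subject's AEs and assess their severity and relationship to study drug. SAP 4.5.1 names the AE rate as the primary endpoint and lists the severe AE rate among the others. Relatedness also drives the halting rules in protocol 4.4.3, where one related grade 4 event, one related death or one related seizure is enough to halt the study temporarily.

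**Working it through.** **1. The plan's own figures.** Protocol 3 and 5.3 give 445 subjects at 4:1.
- 445 × 4/5 = 356 and 445 × 1/5 = 89, as stated.
- PK plus non-PK: 32 + 324 = 356 and 8 + 81 = 89, as stated.
- Detection statement in protocol 7.1: 1 − 0.99^300 = 0.951, as stated (about 95%).

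This point changes none of these.

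**2. The chain, rule by rule.**
- Investigator breaks the code → subject withdrawn (protocol 5.4.2, SAP 4.3).
- Subject withdrawn before completing → may be replaced (protocol 4.4.4, first sentence).
- Subject replaced → same treatment (protocol 4.4.4, second sentence).
- Exception for an unblinded predecessor: none found in the protocol or SAP. The bar on reusing randomisation numbers (5.3) does not help, because a new number does not hide an arm that 4.4.4 has already fixed.

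**3. What must also be true for the arm to be known.** (a) The replacement option is taken up. (b) The newcomer is at the same site. (c) The site can link newcomer to predecessor. Condition (c) is likely, because the investigator is the one who decides on the replacement. Condition (b) is open for the main cohort, where the SAP describes competitive enrolment across sites. It is most plausible in the PK subset, with one or two sites.

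**4. What the knowledge adds.** Best guess of a new subject's arm under 4:1: 4/5 = 0.80. With all three conditions met: 1.00.

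**5. Largest effect on the AE rate.** A code-broken subject who was dosed stays in the Safety Population (protocol 7.2), so a replacement adds to the denominator. With planned arm size n and k such replacements, the rate moves by at most k/(n + k), reached only if every one of them changes status between no AE and at least one AE.

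| k, all in one arm (assumed) | TPOXX, n = 356 | Placebo, n = 89 |
|---|---|---|
| 0 | 0 | 0 |
| 1 | 1/357 = 0.28 points | 1/90 = 1.11 points |
| 3 | 3/359 = 0.84 points | 3/92 = 3.26 points |

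The documents give no code-break or replacement rate, so k is an assumption.

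**6. Which outcomes are exposed.** SAP 9.3 counts a subject once for at least one post-dose AE. Severity and relationship do not enter that count, so the primary rate moves only if knowing the arm changes whether any AE is recorded at all. The severity and relationship tables and the halting rules rest directly on the investigator's assessment.

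**7. Price of a fresh draw.** Expected new randomisations to regain one subject in the lost arm: 1/0.80 = 1.25 for TPOXX and 1/0.20 = 5 for placebo. Against the PK minimum, one lost subject is 1/32 = 3.1% or 1/8 = 12.5%.

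**The case against.** The strongest reply is that the path is guarded in practice. Replacement is optional. The two parties consulted, the medical monitor and the sponsor, are the same two who should already know of the code break, and one of them is charged with keeping the blind. They can advise against replacing. There is also little pressure to replace: the plan randomises about 356 to TPOXX to secure 300 with at least 92% of doses, a margin of 56, and the enrolment totals are floors that ordinary randomisation can fill. The replacement subject stays blinded and keeps a diary, and protocol 6.2.1 requires every AE to be recorded whatever its relationship to study drug.

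Most of this stands, and it is why the expected effect is small. It does not close the gap. As 4.4.4 is written, the consultation concerns whether to replace; once that is agreed the arm follows automatically, and nothing requires the monitor or the sponsor to refuse.

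A reader might go further and infer that 4.4.4 contradicts the blinding sections outright, or that every code break exposes a later subject. The documents do not support either reading. Section 4.4.4 discloses nothing by itself, 5.4.2 already provides for individual emergency unblinding, and the arm becomes known only under the three conditions in step 3. A reader might also infer that same-arm replacement as such invalidates the age-stratified Mantel-Haenszel comparison. That does not follow: after an ordinary withdrawal the investigator remains blinded and learns nothing about the replacement's arm.

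**Conclusion.** The point holds as an unaddressed interaction between protocol 4.4.4 and the code-break rule in protocol 5.4.2 and SAP 4.3. It can defeat concealment and investigator blinding for a particular replacement subject, given replacement at the same site and a visible link to the predecessor. That the text has no exception is certain. Whether a case will arise is not: it should be rare and may never happen.

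The bounds in step 5 assume planned arm sizes, dosed predecessors, all cases in one arm and every affected subject's AE status changed, so the real effect on the primary rate should be smaller. They apply to the Safety Population; the size of the Per-Protocol Safety Population is not fixed in advance. The more realistic exposure is in severity and relatedness assessments, where a single unblinded assessment could bear on a halting rule. No sample size or detection figure is affected. This is a cheap improvement to make, not a flaw that threatens the trial's conclusions.

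**What to change.** Add to protocol 4.4.4: *Treatment is not carried over when the withdrawn subject's assignment has been unblinded to anyone at the site. Any replacement for such a subject is a new randomisation through the IWRS, using the next number in the replacement subject's own age stratum.* Add a matching line to SAP 4.3, which at present does not mention replacements.

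A further sentence in protocol 5.3, saying that other replacements get a new number through the IWRS without the arm being disclosed to the site, is optional; it largely restates what 5.3 already provides. Same-arm replacement for subjects who remain blinded can stay as it is, and the rule withdrawing code-broken subjects is not at issue here.

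**Cost.** Two short text changes, plus a check of how the IWRS handles replacements, since its specification is not in the documents. The downside is that the new subject may fall in the other arm, at the expected number of draws in step 7. This matters mainly for the PK subset, because 5.3 stratifies by age group only and a fresh draw does not protect the minimum of 32 and 8. Those figures are floors, so extra PK subjects can be randomised if a shortfall appears.

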### **5. STUDY TREATMENTS**

#### **5.1 TREATMENTS ADMINISTERED**

Subjects will be randomly assigned to 1 of 2 treatment groups. The treatment groups will be as follows:

- Treatment Group 1: An oral dose of 600 mg (3 × 200-mg capsules) TPOXX BID (every 12 hours [ $\pm$ 30 minutes]) for subjects with a body weight of 120 kg or less or TID (every 8 hours [ $\pm$ 30 minutes]) for subjects with a body weight more than 120 kg for 28 days (Day 1 to Day 28).
- Treatment Group 2: An oral dose of placebo (3 capsules identical to TPOXX) BID (every 12 hours [ $\pm$ 30 minutes]) for subjects with a body weight of 120 kg or less or TID (every 8 hours [ $\pm$ 30 minutes]) for subjects with a body weight more than 120 kg for 28 days (Day 1 to Day 28).

